Fifty-two participants will be enrolled per arm, for a total of 104 patients. Previous studies evaluating interventions for implant bleeding have defined a clinically significant difference as a decrease in bleeding/spotting days by 20-40%.^{22,23} Therefore, our effect size will be a 30% decrease in the amount of bleeding/spotting days. The sample size calculation used for this study assumes a standard deviation of 10, an alpha of 0.05, power of 80%, and accounting for 15% drop-out. This standard deviation is based on a previous study that found the standard deviation for the mean number of bleeding/spotting days to be approximately +/- 10 days.²²

STATISTICAL METHODS

Demographics will be presented with descriptive statistics stratified by randomization group. Student t tests, chi-square, and Fisher Exact tests will be used, where appropriate, to compare characteristics of participants receiving ulipristal acetate to those receiving placebo. For the primary outcome, mean number of bleeding days in the 30 days following intervention, if normally distributed, we will use a t-test. If not normally distributed, the Mann-Whitney U test will be employed. These tests will also be employed for our secondary outcomes of bleeding pattern satisfaction, medication side-effect satisfaction, and contraceptive efficacy. For the secondary outcome regarding cessation of bleeding by day 10, as this outcome is dichotomous, we will use a Chi-square test (or Fisher Exact test, if appropriate).

MISSING DATA

Missing data rates and patterns will be assessed twice weekly by the data manager and remedial measures, including re-abstraction of data and retraining of staff, will be used as needed to minimize missing data.

ETHICAL CONSIDERATIONS

INSTITUTIONAL REVIEW BOARD

Washington University School of Medicine in St. Louis, MO, has applied for and been approved through the Washington University School of Medicine's Institutional Review Board (IRB) office (protocol number #201612002).

INFORMED CONSENT

All participants will be introduced to the study and will be screened for eligibility based on the previously listed inclusion and exclusion criteria. If interested and eligible, potential participants will be given an informed consent form to read and review. Research personnel will then explain the study to the potential participant, outline key risks, benefits, and alternatives (including not participating), and then have participants sign the informed consent form. A copy will be given to the participant and a copy will be kept in the participant's research file.

PARTICIPANT CONFIDENTIALITY

After the informed consent has been signed, each subject will be entered into the enrollment database and be assigned a unique subject identification number. No two subjects will have the same subject identification number. This subject identification number will identify the subject throughout the study and will be used for all source documents, data collection forms, and bleeding diaries. The subject identification number will be held confidential so far as permitted by law. Investigative site staff and, under certain circumstances, the FDA and IRB, will be able to inspect and have access to the subject identification number and the confidential data to which it is linked. Any publication or presentation of data will not contain any identifiable subject information.

SAFETY REPORTS

ADVERSE EVENTS

There are few side effects of UPA and LNG-IUS. These are listed in the protocol and informed consent form. Most side effects resolve spontaneously. Anticipated events means reactions to treatment previously observed that may require medical intervention but are not serious in nature. All adverse events that occur will be recorded in the Source Documents. Adverse Events occurring will be captured and followed until the condition resolves, stabilizes, or is otherwise explained, or the subject is lost to follow-up. Subjects will be instructed that they may contact the PI or study coordinator at any time throughout the course of the study. The Investigator will review each event and assess its relationship to UPA (not related, unlikely, possible, probable, and highly probable). The following definitions will be used for rating relationship to the investigational device:

1. Not related – The event is clearly related to other factors such as the subject's clinical state, therapeutic interventions, or concomitant medications administered to the subject.
2. Unlikely – The event was most likely produced by other factors such as the subject's clinical state, therapeutic interventions, or a concomitant medication administered to the subject; and does not follow a known response pattern to the investigational device.
3. Possible – The event follows a reasonable temporal sequence from the time of investigational device administration; and/or follows a known response pattern to the study treatments, but could have been produced by other factors such as the subject's clinical state, therapeutic interventions, or concomitant medications administered to the subject.
4. Probable – The event follows a reasonable temporal sequence from the time of investigational device administration, follows a known response pattern to the investigational device, and cannot be reasonably explained by other factors such as the subject's clinical state, therapeutic interventions, or concomitant medications administered to the subject.
5. Highly Probable – The event follows a reasonable temporal sequence from the time of investigational device administration, follows a known response pattern to the investigational device, and cannot be reasonably explained by other factors such as the subject's clinical state, therapeutic interventions, or concomitant medications administered to the subject. The event occurs immediately following investigational device administration, improves on stopping the

investigational device, or reappears on repeat exposure. Each adverse event reported will be graded on a 3-point severity scale. The following definitions for rating severity will be used:

6. Mild – easily tolerated, causing minimal discomfort, and not interfering with normal everyday activities.
7. Moderate – sufficiently discomforting to interfere with everyday activities.
8. Severe – incapacitating and/or preventing normal everyday activities.

SERIOUS ADVERSE EVENTS

A serious adverse event is any adverse device experience that results in any of the following outcomes: death, life-threatening adverse device experience, in-patient hospitalization or prolongation of hospitalization, a persistent or significant disability/incapacity, or a congenital anomaly/birth defect. Important medical events that may or may not result in death, be life-threatening, or require hospitalization may be considered a serious adverse device experience when, based upon appropriate medical judgment, they may jeopardize the subject or subject may require medical or surgical intervention to prevent one of the outcomes listed in this definition. If any of the above adverse events are serious as defined by the FDA Code of Federal Regulations (CFR), Title 21, special procedures will be followed. All serious adverse events will be reported within 24 hours of acknowledgment to the Washington University in St. Louis coordinating center, whether or not the serious events are deemed treatment-related. All serious event reporting will adhere to 21 CFR part 812 and the IRB will be notified accordingly. Adverse events, whether serious or non-serious, will be followed until the condition is resolved, stabilized, or otherwise explained, or the subject is lost to follow-up. Adverse events will be captured up to one week after a subject completes the study and where appropriate, medical tests and examinations will be performed to document the resolution of event(s). Outcomes may be classified as resolved, improved, unchanged, worse, fatal, or unknown (lost to follow-up). Following the resolution of any study-associated adverse events there will be no further reports for that subject.

INVESTIGATOR MONITORING

Data will be collected at weekly follow-up appointments and phone follow-up surveys with regards to any side effects experienced during the study medication period. Serum levels of progesterone will also be monitored to assess contraceptive efficacy in a subset of patients. All of this data will be reviewed weekly.

STUDY FLOWCHART

REFERENCES

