Hypothesis: UPA will decrease bleeding and spotting days in users of the ENG implant with unscheduled bleeding by 30% when compared to placebo as assessed by daily bleeding diaries.

SECONDARY AIMS (SA)

SA1: To evaluate bleeding cessation rates by day 10 following seven days of treatment with either ulipristal acetate or placebo.

SA2: To evaluate participant satisfaction with regards to bleeding pattern after use of ulipristal acetate.

SA3: To evaluate participant satisfaction with regards to medication side effects.

SA4: To evaluate effect, if any, of ulipristal acetate on ovulatory status.

KEY STUDY MEASURES

PRIMARY AIM

1. Daily SMS text message bleeding diaries (Day 1 – Day 30)

SECONDARY AIMS

1. SMS text message bleeding diaries Day 1 – Day 10
2. Phone/in-person survey to assess satisfaction with bleeding pattern at 1, 2, 3, and 4 weeks post-study enrollment
3. Phone/in-person survey to assess satisfaction with medication side effects at 1, 2, 3, and 4 weeks post-study enrollment
4. Serum progesterone levels at baseline and at 1, 2, 3, and 4 weeks post-study enrollment

STUDY DESIGN

The INTERRUPT study is a single-site, double-blinded, randomized, placebo-controlled clinical trial. The total sample size for this study is 104. Of these participants, a subset will undergo weekly venipuncture to assess serum progesterone levels.

RANDOMIZATION SCHEME

A block randomization scheme will be created using a computerized random number generator. In order to keep the research team and participants blinded, assignment will be done by the pharmacy based on this randomization scheme. The pharmacy will make identical UPA and placebo capsules, dispensed as a labeled outpatient prescription after a participant is randomized. The randomization scheme will be generated by a random number table with an allocation ratio of 1:1 in blocks of four with a total of 52 participants in each group for a total sample size of 104.

DESCRIPTION OF METHODS

ULIPRISTAL ACETATE

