UPA is a synthetic progesterone receptor modulator, shown to postpone follicular rupture and have mixed agonist/antagonist effects within uterine tissue. The U.S. Food and Drug Administration (FDA) approved Ulipristal acetate in August 2011 as an emergency contraceptive for prevention of pregnancy following unprotected intercourse or a known or suspected contraceptive failure. In other countries, including Canada and Europe, UPA is indicated for the preoperative treatment (*e.g.*, reduction in size for less invasive procedure) and long-term management (*e.g.*, abnormal uterine bleeding) of symptomatic leiomyoma. The likely mechanism of action of UPA for decreasing or stopping progestin-associated excessive bleeding is the displacement of local progestin that counteracts endometrial angiogenesis. The recommended dose ranges from 5-10mg daily for up to three months at a time.

In the United States, UPA is only available in 30mg doses. To ensure feasibility and generalizability, participants will be given 15mg UPA doses, which would allow for splitting of the currently-available UPA tablet if the therapy proves beneficial.

Medication (UPA or placebo) will be taken for seven consecutive days. Participants will be instructed to begin their medication on the day of enrollment (*i.e.*, Day 0) and continue through Day 6.

BLEEDING DIARIES

Participants will completed 30 daily text message bleeding diaries that track medication compliance through Day 6 and any bleeding experienced during the study.

FOLLOW-UP SURVEYS

Weekly follow-up surveys will be conducted to assess participants' compliance with medication, experience of side-effects, as well as their satisfaction with their bleeding patterns at the end of weeks 1, 2, 3, and 4.

VENIPUNCTURE

A subset of participants (*i.e.*, 20 UPA, 20 placebo) will undergo weekly venipuncture to assess serum progesterone levels.

POTENTIAL BENEFITS AND RISKS

POTENTIAL BENEFITS

If UPA is effective, it will decrease the number of bleeding and/or spotting days or lead to amenorrhea. As a result, satisfaction with the contraceptive implant may increase. UPA, however, has not previously been studied as a therapy for unscheduled bleeding with the ENG implant.

POTENTIAL RISKS

Participants may experience one or more of the risks indicated below from their participation in this study. In addition, there may be other unknown risks, or risks that were not anticipated, associated with participation in this study.

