All participants will meet with the study coordinate to enroll in the study. Participants in the progesterone subset will also meet with the MA to give a blood sample.

- Try to schedule the enrollment appointment as soon as possible since the eligibility criteria for bothersome bleeding has a small window (*i.e.*, 24 days). If they are unable to enroll within a week, schedule the enrollment appointment and tell them that you will call the day before the appointment to re-screen them for eligibility.
- The enrollment process will take 45 minutes to 1 hour: 45 minutes for the study coordinator visit and 15 minutes for the blood draw.
- Schedule the enrollment visit in Office Tracker in the “DCR Studies” column.
- Send the participant a confirmation email that includes the date and time of their enrollment appointment, directions to the DCR, and a copy of the informed consent document.
- Call the day before the enrollment appointment to confirm.

ENROLLMENT

We will enroll 104 participants overall, 52 participants receiving UPA and 52 receiving placebo. Of these 104 participants, 40 will participate in the progesterone subset, 20 from each intervention group. Participation in this portion of the study will be voluntary and offered to all subjects until maximum enrollment for each group is met.

INCLUSION & EXCLUSION CRITERIA

Inclusion Criteria

- People age 18-45
- Implant placed >90 days and <3 years prior to enrollment
- Greater than 1 bleeding/spotting episode in a 24-day time period
- Willing to be abstinent or use condoms during the study period
- Willing to complete 30-day bleeding diary (via text)
- Ability to send/receive SMS text message
- Willing to be randomized to placebo or ulipristal acetate

Exclusion Criteria

- Non-English speaking
- Implant placed <90 days or >3 years prior to enrollment
- Contraindication to ulipristal acetate
- Inability or unwillingness to comply with medication protocol
- Inability or unwillingness to comply with bleeding diary
- Current breastfeeding

ENROLLMENT PACKET

The following materials are included in the INTERRUPT study packet:

- An orange 9x12 envelope
- 2 informed consent documents
- Prescription order form
- Bleeding diary answer key
- Tax office form
- Gift cards
- Serum Progesterone Standard Clinical Chemistry Form (if participating in the progesterone subset)

Study packets are stored in the top left drawer of the study coordinator's desk.

BASELINE ENROLLMENT

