The enrollment process includes multiple activities from obtaining consent to providing the participant with a gift card for their time. This section will describe the process in detail and the associated forms that are completed during the enrollment appointment. The enrollment process for the INTERRUPT study must be done in-person.

Order of Enrollment Activities

1. Obtain Informed Consent
2. Complete & Fax Prescription Order Form
3. Collect Contact Information
4. Conduct Baseline Survey
5. Verify Text Messaging Service with Participant's Phone
6. Complete Post-Randomization Form
 - a. Schedule First Phone Follow-Up Survey and/or Clinic Appointment
7. Blood draw from participants in progesterone subset
8. Distribute Medication
9. Complete Tax Office Form & Distribute Gift Cards
10. Wrap-Up

Informed Consent Process

The informed consent process is the most important step of the enrollment process. The informed consent provides the participant with written information regarding (1) study procedures and (2) responsibilities, costs, risks, benefits, and confidentiality related to participating in the study.

The participant provides their signature on the informed consent document, which has been approved by the Human Research Protection Office. This signature indicates they are fully aware of their rights and privileges as a study participant. The informed consent document must be completed in its entirety in order for the participant to move through the remaining steps of the enrollment process. The informed consent document can be read to the participant in its entirety or summarized using key points from each section. You will ask the participant if they would like it read to them in its entirety or summarized.

Steps to Take When Obtaining Informed Consent

- Give them a copy of the informed consent document to review
- Provide a brief explanation of the informed consent
- Explain that you will leave the room to give them 10 minutes (or more should they request it) to read the form before you return and go over the document together
- Once back in the room, offer to read the informed consent document verbatim or summarize the main points

- All study participants need to record their initials for two different statements
 - On page 2, those participating in the progesterone subset will initial, “Yes” in order to have their blood drawn. Participants in the standard subset will initial, “No.”

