 - On page 7, all participants will initial “Yes” or “No” based on their preference for being contacted by email.
- When finished, the study coordinator must sign and date both the participant’s copy and their own copy
- The participant signs and dates the consent form
- Give the participant the informed consent form signed only by the coordinator
- The completed consent form with the participant’s signature goes in the enrollment packet

Prescription Order Form

The prescription order form will need to be faxed to the IDS pharmacy in order for the participant to be randomized to receive either UPA or placebo.

- Complete the prescription order form with the participant’s full name, date of birth, and known allergies
- Add the subject ID, which will be written with three digits (e.g., 001)
- Write the correct date
- Fax the prescription order form, along with the signature page of the informed consent document, to the pharmacy
- Put the original prescription order form and the fax confirmation sheet in the study packet.

Contact Information Form

Contact information is obtained at the time of the enrollment for follow-up purposes. We obtain contact information of the participant and one close friend or relative, who will act as an alternate contact if we are unable to get in touch with the participant.

- Enter the information directly into RedCap

Baseline Questionnaire

The study coordinator administers the baseline questionnaire to every participant during the enrollment visit. They will ask the participant to respond to the baseline survey questions based on their experiences to date with their current implant. Below is the process to complete the baseline questionnaire:

- Complete the baseline survey in RedCap
- Open participant’s research file
- Click the “Date” button

- Administer the survey
- At the end of the survey, select “Complete” from the dropdown menu, click “Save”, and tell the participant that they will receive a text message shortly

Verification of Text Message Service

Once the baseline questionnaire is completed, the participant will be automatically sent a text message from the text messaging service (Twilio) to verify that they able to receive the daily bleeding diaries. If they respond to the text message, a check mark will automatically appear next to the link for the “Text Verification” form in RedCap.

Post Randomization Form

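### Closing the progesterone subset arm by arm works against the blind: held to exactly 20 per arm, it would sort some willing women by arm in the coordinator's view

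*Combined protocol and SAP*

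**What the plan says.** The opening paragraph of Enrollment, under Study Procedures, sets the target: "40 will participate in the progesterone subset, 20 from each intervention group". The Venipuncture paragraph under Description of Methods repeats the split. Enrollment then gives the closing rule: "Participation in this portion of the study will be voluntary and offered to all subjects until maximum enrollment for each group is met".

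Randomization Scheme, under Study Design, states the blind: "In order to keep the research team and participants blinded, assignment will be done by the pharmacy based on this randomization scheme". It describes the list as an "allocation ratio of 1:1 in blocks of four with a total of 52 participants in each group" and mentions no stratification.

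The order of steps is set out under Baseline Enrollment. Consent is step 1, and on the consent form "those participating in the progesterone subset will initial, “Yes” in order to have their blood drawn". Step 2 is the order form: "The prescription order form will need to be faxed to the IDS pharmacy in order for the participant to be randomized". The instructions for it begin "Complete the prescription order form with the participant’s full name, date of birth, and known allergies" and add the subject ID and the date. Subset status is not among the items listed.

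The study coordinator enrolls all participants and administers the weekly surveys (Follow-Up and Retention). The coordinator also follows up and fills in missed diary days (Monitor Bleeding Diaries). At subset visits this is done from the participant's recall (Bleeding Diary Review).

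**The concern.** A blinded team cannot count subset members by arm. The plan names nobody else to do it and describes no message from the pharmacy to the site. If the per-arm maximum is nevertheless enforced, someone who holds the code must say whether each willing woman may join once one arm is full. A refused woman is then in the full arm and an accepted woman is in the open arm.

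The coordinator would see the result, because subset status decides whether blood is drawn, whether follow-up is in person or by phone, and the value of the gift cards. The same coordinator collects the two satisfaction outcomes and the part of the primary-outcome diary that was missed by text. All of these are self-reported, so the blind is their main protection against interviewer influence. Blocks are also fixed at four in the manual that staff use, so knowing one woman's group changes the odds for others in her block.

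The order of steps adds a difficulty. The woman has already initialled her choice before she is randomized. Refusing her by arm would need either an early look at the next allocation or her removal from the subset after assignment.

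**Working it through.** The plan gives no power or precision calculation for the subset, so there is no figure to reproduce. The check is how many women an exact 20-per-arm rule would sort.

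**Inputs from the plan.** 104 women; 1:1 allocation in blocks of four (104/4 = 26 blocks); maximum of 20 per arm in the subset; no stratification stated.

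**Assumed input.** The chance that a woman is willing to join. The documents give none, so a range of 50% to 90% is used.

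**Method.** 40,000 simulated trials per setting (10,000 for the 90th percentiles). Each woman volunteers independently. An arm's subset closes at 20. The sorted women are the volunteers seen after the first arm fills, up to and including the one who fills the second arm. Each of them is either refused (full arm) or accepted (open arm).

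| Willing | Mean sorted | 90th percentile | Mean refused | Trials with at least one refusal |
|---|---|---|---|---|
| 50% | 6.8 | 14 | 3.2 | 82% |
| 60% | 6.4 | 13 | 2.9 | 80% |
| 75% | 5.1 | 10 | 2.2 | 75% |
| 90% | 3.4 | 7 | 1.3 | 63% |

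**Exact check at 100% willingness.** The first 40 women make 40/4 = 10 complete blocks, so nobody is refused. In the tenth block the first arm fills at the second woman with probability 1/3, leaving two women sorted, and otherwise at the third, leaving one. The mean is (1/3 × 2) + (2/3 × 1) = 1.33, and the simulation gives 1.33.

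**Looser reading.** If the offer stays open to everyone until both arms reach 20, nobody is accepted or refused by arm. The subset then exceeds 40 by about 1 to 3 women on average over the same range of willingness.

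**Single cap of 40 in total.** The split is exactly 20/20 in 18%, 20%, 25% and 37% of trials at 50%, 60%, 75% and 90% willingness. The 95th percentile of the larger arm is 24, 24, 23 and 22. Precision relative to 20/20, for a difference between two means with equal variance, is (1/20 + 1/20) / (1/n1 + 1/n2):

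- 22/18: 0.1 / (1/22 + 1/18) = 0.99
- 24/16: 0.1 / (1/24 + 1/16) = 0.96

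**Stratifying by subset choice.** The subset takes 40/4 = 10 complete blocks, giving 20/20. The other 64 women take 64/4 = 16 complete blocks, giving 32/32. The totals are 20 + 32 = 52 per arm, as planned.

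**The case against.** The strongest reply is that the leak is inferred. No section says that the pharmacy reports arm counts, announces a full arm or rules on individual women. The order form as described does not even tell the pharmacy who is in the subset. A choice made before randomization cannot by itself reveal an arm. This stands as a limit: the plan states a rule whose exact enforcement would cost part of the blind, but it does not describe that enforcement.

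A reader might infer that the coordinator would learn each sorted woman's treatment. The documents do not support that. Acceptance or refusal shows only full arm or open arm, and the label UPA or placebo follows only if staff also learn which arm filled. Without that, two unlabelled groups are separated, which is a weaker breach.

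A reader might also infer that blinded staff could follow the rule only by ignoring it. That goes too far. The closing sentence can be read as keeping the offer open to all until both arms are full, which reveals no woman's arm by acceptance or refusal. However, that reading conflicts with the stated 40 and still needs an unblinded counter. The 20/20 target itself is also compatible with the blind if the pharmacy stratifies.

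Finally, the exposure is small. The main diary route is the participant's own same-day text reply, so only missed days pass through the coordinator. Nothing suggests that participants are unblinded.

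**Conclusion.** The point holds as a conflict between a stated closing rule and the stated blind, and it should be resolved. Enforced exactly, the rule would sort about 3 to 7 of 104 women on average by arm (90th percentile 7 to 14) in view of the person who collects self-reported outcomes. These figures rest on assumed willingness of 50% to 90%, on independent volunteering, and on the rule being applied woman by woman.

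The count measures exposure, not bias. No effect on any endpoint has been estimated, and the documents do not support a claim that the primary result would be compromised. The text needs correcting on either reading, because each needs arm counts that the blinded team cannot hold.

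**What to change.** Remove the per-arm closing rule from Enrollment, amend the matching split under Venipuncture, and choose one of two replacements.

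1. **Single cap.** For example: *The subset is offered to consecutive women until 40 in total have agreed to join. Study staff receive no counts by arm, and the achieved split will be reported.* The cost is a slightly uneven split. A 24/16 split, at the upper end of the 95th percentiles above, keeps 96% of the precision for the ovulation aim (SA4).
2. **Stratified blocks.** Add subset status to the prescription order form, have the pharmacy run separate blocks of four for women who choose the subset at consent, and stop at 40. This keeps 20/20 in the subset and 52/52 overall without arm counts at the site. The cost is one extra stratum and one form field. If fewer than 40 women volunteer, a last incomplete block can leave the arms of a stratum at most two apart.

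The first option is the simpler. The second is preferable if exactly 20 per arm matters to the investigators.
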